1.2.2 Enzalutamide

Enzalutamide is an androgen receptor inhibitor that acts on different steps in the androgen receptor signalling pathway. The chemical name is 4-{3-[4-cyano-3-(trifluoromethyl)phenyl]-5,5-dimethyl-4-oxo-2-sulfanylideneimidazolidin-1-yl}-2-fluoro-*N*-methylbenzamide. The molecular weight is 464.44 and molecular formula is C21H16F4N4O2S. Enzalutamide is a white crystalline non-hygroscopic solid. It is practically insoluble in water.

Enzalutamide has been shown to competitively inhibit androgen binding to androgen receptors and inhibit androgen receptor nuclear translocation and interaction with DNA. A major metabolite, N-desmethyl enzalutamide, exhibited similar *in vitro* activity to enzalutamide. Enzalutamide decreased proliferation and induced cell death of prostate cancer cells *in vitro*, and decreased tumour volume in a mouse prostate cancer xenograft model.

Following oral administration (160 mg daily) in patients with metastatic castration-resistant prostate cancer, the median time to reach maximum plasma concentrations (Cmax) is 1 hour (range 0.5 to 3 hours). At steady state, the plasma mean Cmax values for enzalutamide and N-desmethyl enzalutamide are 16.6 µg/mL (23% CV) and 12.7 µg/mL (30% CV), respectively, and the plasma mean predose trough values are 11.4 µg/mL (26% CV) and 13.0 µg/mL (30% CV), respectively. With daily dosing enzalutamide steady state is achieved by Day 28, and enzalutamide accumulates approximately 8.3-fold relative to a single dose. Daily fluctuations in enzalutamide plasma concentrations are low (mean peak-to-trough ratio of 1.25). At steady state, enzalutamide showed approximately dose proportional pharmacokinetics over the daily dose range of 30 to 360 mg. The plasma pharmacokinetics is adequately described by a linear two-compartment model with first-order absorption.

In vitro, CYP2C8 and CYP3A4 are responsible for the metabolism of enzalutamide. Based on *in vivo* and *in vitro* data, CYP2C8 is primarily responsible for the formation of the active metabolite (N-desmethyl enzalutamide). Enzalutamide is primarily eliminated by hepatic metabolism. The mean terminal half-life (t1/2) for enzalutamide in patients after a single oral dose is 5.8 days (range 2.8 to 10.2 days) (R13-5391). Please also refer to the current summary of product characteristics (SPC) from eMC website.

Boehringer Ingelheim BI Trial No.: 1280.8 Doc. No.: c02304008-15

06 Jun 2022

Page 27 of 241

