4.1.4.3 Enzalutamide (Phase Ib and Phase II- Arm A and B)

On the days of infusion, the enzalutamide dose (160mg daily) should be taken in the clinic immediately after the start of the infusion of BI 836845. On all other days patients must take the recommended enzalutamide dose of 160 mg daily, as per the SPC at the same time of day and preferably in the morning.

On the days of PK sampling, enzalutamide must be taken in the clinic, and not at home.

For countries where enzalutamide is supplied, enzalutamide packs will be allocated by the IRT system for every weekly visit and/or the start of every cycle dependent on the part of the trial to which the patients are entered. The supply will cover either a full week (7 days), or a full cycle (28 days), of treatment. Back-up packs will be provided. Replacement packs will also be available for supplies that might be lost by the patient, or where there might be a delay in the first visit of a cycle.

During the COVID-19 pandemic, physical visits to the sites may need to be restricted to ensure patient's safety. Based on a thorough assessment of the benefits and risks, the investigator may still decide to continue the trial treatment and trial medication may be shipped to the patient's home if acceptable according to local law and regulations. The

Doc. No.: c02304008-15 Trial Protocol Version 12 Page 50 of 241

Proprietary confidential information. © 2022 Boehringer Ingelheim International GmbH or one or more of its affiliated companies. All rights reserved.

shipment should occur via a courier approved by the sponsor in order to ensure correct conditions of shipment.

4.1.4.4 Temporary treatment interruption and dose reduction for BI 836845 and enzalutamide during phase Ib and phase II

Drug-related DLTs or those adverse events requiring dose adjustment, will be managed by a pause in treatment followed by a subsequent dose reduction of the relevant medication according to tables 4.1.4.4:1 and 4.1.4.4:2. In phase Ib escalation, BI 836845 and enzalutamide must be paused when a drug-related DLT occurs regardless of the cycle of treatment. In the phase Ib exploratory expansion cohort and phase II, the causal drug(s) should be paused regardless of the cycle of treatment. In both phase Ib and phase II, the patient will be kept on study until both BI 836845 and enzalutamide are permanently stopped and the patient is discontinued.

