5.2.6 Electrocardiogram

5.2.6.1 ECG Recording – Phase Ib and Phase II

Triplicate 12-lead ECGs (each ECG to be taken approximately 2-3 minutes apart) will be performed in all patients at the time-points as specified in the Flow Chart and Appendix 10.6 and will be coincident to PK sampling. The investigator will review the ECG recording, comment on any clinical significance and if applicable record any ECG abnormality that meets AE criteria.

Triplicate ECGs will be recorded at the following time-points:

- Screening
- Pre-dose (-20 min. to -5 min. before administration of BI 836845 and/or enzalutamide) and immediately after the end of infusion of BI 836845 (within 15 minutes after the end infusion to ensure PK sampling is also completed within 15 minutes), or one hour after the administration of enzalutamide on the following days*:
 - o **Cycle 1:** Day 1, Day 8, Day 15
 - o **Cycle 2:** Day 8, Day 15
 - o **Cycle 3:** Day 1, Day 8, Day 15
 - O Cycles 6, 9, 12 and in 12 weeks intervals thereafter on Day 1
- EOT
- First follow-up visit only
- * ECGs to be taken prior to PK sample time-points where applicable. See appendix 10.6 for ECG flowchart.

ECGs will only be correlated to PK for the drug combination (BI 836845 and enzalutamide) during phase Ib and phase II arm A.

All ECGs will be recorded digitally with ECG equipment provided by a CRO ECG core lab.

Before study start the study sites will be trained for the proper use of the equipment and transfer of the electronic data to the CRO core lab. To be able to assess the electrocardiographic variables in resting phases the ECGs have to be recorded in supine position after the subjects were at rest for at least ten minutes. At specific time-points triplicate ECGs will be recorded to minimize the physiologically induced QT and heart rate variability. The recordings will be evaluated at the site by the investigator (or delegate) to assess any ECG abnormalities and changes in interval duration. ECG abnormalities will be

Doc. No.: c02304008-15 Page 73 of 241 Proprietary confidential information. © 2022 Boehringer Ingelheim International GmbH or one or more of its affiliated companies. All rights reserved.

carefully monitored and, if necessary, the subject will be removed from the trial and medically treated.

All ECGs will be sent to the CRO core lab to centrally and independently evaluate the electrocardiograms.

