model the within-patient measurements on each day (pre- and post-dose measurements). A second two-by-two unstructured covariance matrix will be used to model the within-patient measurements between days; this matrix will be the same for all combinations of days. Hence, in this second analysis the number of necessary covariance parameter estimates will not depend on the number of included timepoints. The sensitivity analysis will be restricted to the endpoints based on the QTcF interval. The model is detailed in Section 9.2.2.

Exposure-response analyses (Phase I and Phase II parts pooled)

The exposure-response analyses will be based on the ECG-PK set. The analyses will include the pooled data of the Phase I and Phase II parts. Patients in the expansion cohort of the Phase I part will be excluded as they are pre-treated with enzalutamide. Data of patients receiving enzalutamide alone (Phase II part) will be included with xentuzumab plasma concentrations set to zero (see R17-0553).

Pairs of xentuzumab plasma concentrations and QTcF changes from baseline that are not time-matched (i.e. a time deviation between PK blood sampling and ECG recording that is not acceptable, see Section 6.6.5) will be excluded from the analyses. When the collecting time of the blood sample or the ECG recording is not available, the pair will also be excluded. The decisions to exclude pairs from the analyses will be made no later than at the final BRPM before DBL (for further details see also Sections 6.3 and 6.6.5).

The relationship between xentuzumab plasma concentrations and QTcF change from baseline will be explored using a random coefficient model including a categorical variable 'treatment' with the two levels 'xentuzumab+enzalutamide' and 'enzalutamide' to estimate the adjusted mean difference between 'xentuzumab + enzalutamide' and 'enzalutamide' in QTcF change from baseline and its 90% confidence interval at clinically relevant plasma concentrations, which are the geometric means of the C1D1_{1h}, C2D8_{1h} and C3D1_{1h} values of the RP2D. The model is detailed in Section 9.2.3. For visualization, plasma concentration against QTcF changes from baseline will be plotted, as well as the (fixed effect) regression line, its 90% confidence interval and the geometric means of C1D1_{1h}, C2D8_{1h} and C3D1_{1h}.

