The assumption of a linear relationship will be checked by visual inspection of diagnostic plots (presented in Section 16.1.9.2 of the CTR). If linearity is not given, the concentrations may be log-transformed prior to the analysis.

To inspect (graphically) whether the peaks of the time-profiles for xentuzumab plasma concentrations and QTcF interval changes from baseline coincide, figures of the individual time profiles of xentuzumab plasma concentrations and QTcF interval changes from baseline will be generated for each patient (presented in Appendix 16.1.9.2 of the CTR), as well as for the means of the group treated at RP2D/MTD (presented in Section 15 of the CTR). Mean time profiles from the patients treated with enzalutamide alone will be displayed as well.

These analyses will also be performed using the corresponding endpoints based on the QT interval and heart rate.

Furthermore, a first sensitivity analysis will be performed using the random coefficient model described above including the categorical effect 'day', and a second sensitivity analysis will be done including the categorical effect 'time' with the two levels pre- and post-dose, instead. These analyses will only be applied to the QTcF changes from baseline.

Appropriateness of QT interval correction methods for heart rate

To evaluate the appropriateness of the heart rate correction methods of QT interval, slopes of the relationship of QT, QTcF, and QTcB interval versus RR interval (values log-transformed using the natural logarithm) will be estimated by applying a random coefficient model (see Section 9.2.4) separately for the treatments 'xentuzumab+enzalutamide' and 'enzalutamide'. These analyses will be based on the on-treatment single ECGs (i.e. three values per time point). A table of the resulting (fixed effect) slopes will be displayed together with two-sided 95% confidence intervals in Appendix 16.1.9.2 of the CTR.

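### On the visible text, the main xentuzumab concentration–QTcF model has no time term, so part of a QTcF change shared by both arms is attributed to xentuzumab, and each sensitivity model corrects only one time dimension

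*SAP*

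**What the plan says.** The exposure-response part of SAP 7.8.4 describes its main model as follows: "The relationship between xentuzumab plasma concentrations and QTcF change from baseline will be explored using a random coefficient model including a categorical variable 'treatment", whose two levels are combination and enzalutamide alone. The planned result is the adjusted arm difference with a 90% confidence interval at three post-dose concentrations: the geometric means at C1D1, C2D8 and C3D1, one hour. For the control arm, "Data of patients receiving enzalutamide alone (Phase II part) will be included with xentuzumab plasma concentrations set to zero". The same analyses are repeated for QT and heart rate.

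Two sensitivity analyses follow, for QTcF only. The first adds day to the model just described. Then "a second sensitivity analysis will be done including the categorical effect 'time' with the two levels pre- and post-dose, instead". For the equation the reader is told: "The model is detailed in Section 9.2.3". That section is not in the public text.

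The timing comes from the protocol. On infusion days, "the enzalutamide dose (160mg daily) should be taken in the clinic immediately after the start of the infusion of BI 836845" (Section 4.1.4.3). The post-dose ECG is taken at the end of the one-hour infusion, "or one hour after the administration of enzalutamide on the following days" (Section 5.2.6.1). Section 1.2.2 gives a median enzalutamide time to peak of 1 hour and adds: "With daily dosing enzalutamide steady state is achieved by Day 28, and enzalutamide accumulates approximately 8.3-fold relative to a single dose".

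SAP 7.8.4 also plans a separate Phase II repeated-measures model, which does contain timepoint and treatment-by-timepoint.

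**The concern.** A term that is added only for sensitivity is not in the main model. With concentration fixed at zero and a treatment level of their own, control patients cannot inform the concentration slope. It is estimated only from concentration changes in combination patients, and those changes coincide with other things. The xentuzumab peak falls about one hour after the enzalutamide dose, and both drugs accumulate over the first weeks.

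A QTcF change caused by enzalutamide or by time of day occurs in both arms, but in the combination arm it moves with xentuzumab concentration. The randomised control could separate the two, yet a model without time terms does not use it for that. A shared rise would look partly like a xentuzumab effect, and a shared fall could partly hide a real one. The QT and heart-rate versions have no time-adjusted check at all.

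**Working it through.** The documents state no numerical result for this model, so there is no figure to reproduce.

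**Inputs from the documents**
- 40 patients per arm (Protocol 3.3).
- ECG days: C1 D1, D8, D15; C2 D8, D15; C3 D1, D8, D15; each pre- and post-dose (Protocol 5.2.6.1).
- Xentuzumab: volume 5.8 L, clearance 0.5 mL/min, half-life about 6 days, about 1.5-fold accumulation (Protocol 1.2.1). Consistency check: ln 2 × 5800 mL / 0.5 mL/min = 8041 min = 5.6 days.
- Weekly dose of 1000 mg, used for scaling only (Protocol 4.1.3.1).

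**Assumptions not in the documents:** the size of any shared QTcF change, and all variance components.

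**Step 1, by hand.** Each infusion adds 1000 mg / 5.8 L = 172.4 µg/mL. Accumulation of 1.5 means weekly retention of 1/3. At steady state the post-dose level is 172.4 / (1 − 1/3) = 258.6, the pre-dose level is 86.2 and the mean is 172.4. Let both arms share a pre-to-post shift d, with no xentuzumab effect.
- Slope in the combination arm: d / 172.4 per µg/mL, the whole shift.
- Control mean: d/2, because half its ECGs are post-dose. The combination fit at its mean concentration is also d/2.
- Arm difference at concentration c: d × (c − 172.4) / 172.4.
- At C1D1 1h (172.4): 0. At C2D8 or C3D1 1h (about 258.6): d × 86.2 / 172.4 = 0.50d.

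**Step 2, exact expectation.** I computed the expected generalised least squares fit with random intercept and slope and true xentuzumab effect zero. Weekly retention was 1/3 or 0.445 (6-day half-life), with or without the C1D1 pre-dose record. Drift followed a 5.8-day half-time. The table gives the spurious arm difference at C2D8 1h and C3D1 1h, in ms:

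| Shared change (assumed) | Main | + day | + time | day and time together, or time point |
|---|---|---|---|---|
| Pre-to-post, 5 ms | 2.5 to 2.7 | 2.6 to 2.9 | 0.0 | 0.0 |
| Between-day drift, 5 ms | 0.1 to 0.9 | 0.0 | 0.7 to 1.5 | 0.0 |
| Both | 2.7 to 3.5 | 2.6 to 2.9 | 0.7 to 1.5 | 0.0 |

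For the 5 ms pre-to-post shift, the main model's spurious difference at C1D1 1h is −1.0 to +0.4 ms. Its spurious slope is 2.26 to 2.87 ms per 100 µg/mL. Times 1.724, that is 3.9 to 4.95 ms per infusion increment, or 78% to 99% of the shift. All these results scale linearly with the assumed change.

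**Step 3, error rate of the planned contrast.** The simulation used 40 + 40 Phase II and 12 escalation patients, 200–300 trials per scenario. Time on treatment followed the planned median PFS of 4.6 and 3 months. Assumed SDs: 9 ms within patient, 9 ms intercept, 1.5 ms slope per C1D1 peak.

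| Shared pre-to-post change | Shift at C3D1 1h | 90% interval excludes zero |
|---|---|---|
| 1 ms | +0.5 ms | 11% |
| 2 ms | +1.0 ms | 14% |
| 3 ms | +1.6 ms | 20% |

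Normal check of the last row with SE 2.06: 1.6 / 2.06 = 0.78, and P(Z > 1.645 − 0.78) + P(Z < −1.645 − 0.78) = 0.19 + 0.01 = 0.20.

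**Step 4, with the time point added.** The spurious slope and arm differences are 0.0 ms in every shared-change scenario run. The SE at C3D1 1h goes from 2.05 to 2.08 ms in the exact calculation (2.08 / 2.05 = 1.015) and from about 2.06 to 2.10 ms in the simulation (2.10 / 2.06 = 1.019).

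**The case against.** Several points on the other side stand.

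- A reader might infer that all of a shared change is credited to xentuzumab. That is close to true of the slope but not of the planned estimate, where the treatment term and the control mean absorb about half at C2D8 and C3D1 and most or all at C1D1.
- A reader might quote the simulated rates at which the slope's 90% interval excludes zero: about 39%, 84% and 99% for 1, 2 and 3 ms. The SAP names no slope test and plots the regression line only for visualisation. The planned contrast gives 11% to 20%.
- A reader might infer that no planned analysis handles a pre-to-post change. A constant one is fully removed by the second QTcF sensitivity model.
- This is not the only QTcF comparison. The Phase II repeated-measures model compares arms at each time point, so shared change cancels. It is also run for QT and heart rate. However, it covers Phase II only and gives no concentration-response estimate.
- Large shared changes driven by enzalutamide are hard to reconcile with Protocol 1.2.2, which calls daily fluctuation low: peak-to-trough ratio 1.25, mean peak 16.6 and trough 11.4 µg/mL. If effect is proportional to concentration (an assumption), the daily swing is (1.25 − 1) / 1.25 = 20% to (16.6 − 11.4) / 16.6 = 31% of the peak effect. A 3 ms swing then implies a total effect of about 3 / 0.31 = 10 to 3 / 0.20 = 15 ms. A time-of-day effect remains possible, but the documents give no size for it.
- Section 9.2.3 could define the model more fully. A time term there would, however, sit oddly with the sensitivity analyses in 7.8.4, which add day and time one at a time.

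**Conclusion.** The point holds in limited form. On the visible text the main model has neither day nor pre/post time, and no planned concentration model fits both. The planned contrast at C2D8 and C3D1 would then carry about half of a shared pre-to-post change. The time model leaves about 0.7 to 1.5 ms of an assumed 5 ms drift, and the day model leaves the pre-to-post part. If the two disagree, the visible text gives no rule for choosing between them.

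The documents do not support saying that the QTcF assessment as a whole is unreliable: the analysis is exploratory, the expected bias is modest, and the repeated-measures comparison is unaffected. Confidence is moderate. It rests on the unseen Section 9.2.3, on assumed shared changes and, for the error rates, on assumed variances. Changing the variances did not alter the main- or time-model bias for a 5 ms pre-to-post shift, the one case checked.

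**What to change.** First check Section 9.2.3. If it has no time term, amend SAP 7.8.4 and 9.2.3. Add nominal time point (day by pre-/post-dose, or day and pre/post time together) as a categorical fixed effect common to both arms. Do this in the main concentration–QTcF model and in the QT and heart-rate versions. Keep treatment, concentration and the patient random coefficients. Report the arm differences and 90% intervals from that model, and keep the model without time terms as a sensitivity analysis. If late visits are too sparse to fit, the time-point cut-off already set for the repeated-measures analysis can be used.

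The cost is a line of model text and code, a few extra parameters and intervals about 1–3% wider. No new data are needed.

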7.8.5 Others

Not applicable.

7.9 STATISTICAL BIOMARKER AND PK/PD ANALYSES

The biomarkers collected in different parts of the trial will be analyzed and reported separately for each part of the trial.

As statistical biomarker analyses are purely exploratory, there will be no strict error control in a confirmatory sense.

If data is available, the following biomarkers will be evaluated and reported in the CTR:

7.9.1 Potentially prognostic biomarkers

- Baseline measurements of free, dissociable and total IGF-1, free, dissociable and total IGF-2, total IGFBP-3 in serum and IGF bioactivity in heparin plasma
- Mutational status of archival FFPE tumour samples
- mRNA expression of IGF pathway related genes, e.g. tumour IGF-1 and IGF-2
- Relevant biomarkers related to IGF-1 and IGF-2 downstream cascade (e.g. pAkt) in tumour tissue
- IGF-1/2 protein expression in FFPE tumour sample.
- CTC baseline measurement
- cfDNA baseline measurement

Statistical analyses for prognostic biomarkers

A Kaplan-Meier analysis (including median, 95% confidence interval, Q1 and Q3 statistics) plus corresponding plot will be conducted for PFS.

The categorised/binary biomarker variables for the biomarkers mentioned above will be the group determining factors. Categorisations will be data-driven and described in the URPM minutes and/or in the CTR. For mutational status the focus will be on mutations with known functional impact. For mutational status, mRNA and cfDNA the categorisations defined in the Biomarker SAP (c09122174-01) will be used as starting point for this exploratory analysis.

Cox proportional hazard analysis will additionally be conducted for biomarker-efficacy relationship. The validity of the underlying assumptions will be checked.

Corresponding sensitivity analyses, such as modelling with continuous biomarker variable may also be conducted. Further analyses may be carried out in an explorative approach and results will be discussed in the context of pharmacokinetic, efficacy, and safety data of xentuzumab in combination with enzalutamide.

7.9.2 Purely exploratory biomarkers

The following biomarkers will be listed in the CTR:

- Ki67 expression level in fresh tumour biopsies taken before and after treatment with xentuzumab
- Other exploratory biomarkers measured in fresh tumour biopsies

7.9.3 Biomarker measurements taken over time

Time series analyses will be performed on the following biomarkers:

- For relevant IGF down-stream cascade biomarkes measured in PRP, total IGF-1, total IGF-2, dissociable IGF-1, dissociable IGF-2, free IGF-1, free IGF-2, IGF bioactivity, as well as IGFBP-3 measured in peripheral blood overtime plots and descriptive statistic tables for the measured values and absolute changes from baseline will be created. Baseline values will be derived and all pre-dose values will be flagged. Correlation plots will be shown, Pearson and Spearman correlation coefficients will be calculated. If feasible, exploratory analyses including (non-)linear function fits such as population E_{max} model will be applied. Further details will be provided in the CTR.
- cfDNA concentrations from patient plasma samples assessing mutational profiling at baseline and monitoring mutational status over time of treatment. Exploratory analyses including nonlinear function fits and AUECs (Area Under the Effect Curve) will be performed if feasible (for the calculation, the linear trapezoidal method is used, as described in (3), RD_01). The measures will be compared between the treatments.
- CTC measures over time (overdispersed count data). Exploratory analyses including nonlinear function fits and AUECs will be performed in order to quantify the time for which the cell counts remain under 5 cells per 7.5ml for each patient. The measures will be compared between the treatments.

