An exploratory expansion cohort will be pursued in approximately 25 enrolled patients to ensure 21 evaluable patients at the MTD, and/or recommended phase II dose (RP2D) determined in the escalation part of phase Ib described above. A patient is considered evaluable if data for the assessment of the primary endpoint is available. Patients recruited to this cohort will be on ongoing enzalutamide therapy and be beginning to show a rise in PSA (as described in section 3.3.2 inclusion #19) on this treatment at the time of consent for the expansion cohort of the study. These patients will continue to receive enzalutamide from the first day of treatment on the study combined with BI 836845. Patients in this expansion cohort will continue treatment until disease progression, undue toxicities, or discontinuation for any other reason, see section 3.3.4 for details.

Phase II - Randomised phase II:

In phase II, 80 patients will be randomised in a 1:1 ratio to receive treatment with either BI 836845 plus enzalutamide (Arm A) at the MTD, and/or the recommended phase II dose (RP2D) determined in phase Ib escalation, or enzalutamide alone (Arm B), in an open label, parallel group study design. Patients will continue treatment until disease progression, undue toxicities, or discontinuation for any other reason, see section 3.3.4 for details.

After discontinuation of all trial drugs and completion of the final follow up visit, see section 6.1.3, patients will be followed up further (every 90 days after the last follow up visit) for survival status in an observation period (until approval of protocol version 10 after which no further survival status will be collected).

Doc. No.: c02304008-15 Trial Protocol Version 12 Page 35 of 241

Proprietary confidential information. © 2022 Boehringer Ingelheim International GmbH or one or more of its affiliated companies. All rights reserved.

Phase I and Phase II:

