	At C2D1, site staff must question the patient as to the date, time and dose of last enzalutamide intake prior to the visit; this information must be recorded in the eCRF.

Doc. No.: c02304008-15

Page 92 of 241

 $Proprietary\ confidential\ information. ©\ 2022\ Boehringer\ Ingelheim\ International\ GmbH\ or\ one\ or\ more\ of\ its\ affiliated\ companies.\ All\ rights\ reserved.$

	In Phase Ib expansion cohort only - Review of diary card and compliance check of enzalutamide taken 7 days prior to C2 D1.
Circulating tumour cells (CTCs)	As per the time-points on the Flow Chart and Appendix 10.6: Prior to study drug administration at C1D1, C2D1, C3D1, C5D1, C7D1 and every 12 weeks thereafter at C10D1, C13D1 onwards (until approval of protocol version 10).
Prostate Serum Antigen (PSA)	Single blood sample collected prior to dosing at C1D1, C3D1 and at the start of the cycle thereafter as per the Flow Chart.
Tumour assessments and bone scans	Every 8 weeks (every 2 cycles) up to week 24 and then every 12 weeks (every three cycles) thereafter from start of study treatment in phase Ib escalation and expansion cohort and from randomisation in phase II, i.e. within 7 days prior to theoretical C3, C5, C7, C10 and onwards. Following implementation of Protocol Version 12 as per standard of care.
	Assessment by modified RECIST criteria version 1.1 (R09-0262) and prostate cancer clinical trials working group (PCWG2) criteria, (R13-1642) see appendix 10.4 and section 5.1.2.1
Adverse event and concomitant therapy	Collection of data throughout study treatment period until after approval of protocol version 10 when only adverse event data will be collected.

Trial Protocol Version 12

Page 93 of 241

Proprietary confidential information. © 2022 Boehringer Ingelheim International GmbH or one or more of its affiliated companies. All rights reserved.

From cycle 3 onwards for phase Ib and phase II – the assessments and dosing schedule will be repeated for all subsequent cycles unless otherwise stated in the Flow Chart, e.g. tumour assessment schedule.

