Due to the inherent difficulties determining radiographic progression in this indication, a central imaging unit is employed to interpret the radiographic images and obtain an independent tumour assessment in addition to the investigator's assessment. However, due to these difficulties, there is potentially a high discordance rate between the independent review and the investigators (fewer independent review events compared to investigator assessed events). From Table 7.6: 2 it can be seen that having a discordance rate of going up to 33% – leaving potentially only 40 independent review events – still gives a probability of between 0.66 and 0.74 (corresponding true underling HR of between 0.65 and 0.70) of observing a HR of less than 0.8 in the evaluation of the independent review as well. If the true underlying HR should be 1.0, then the probability of observing a HR of 0.8 is still sufficiently low with 0.24.

Due to the patients' advanced condition and previous treatment regiments obtained before joining this study, the estimated median PFS time in the enzalutamide arm is around 3 months, and between 4.3-4.6 months in the combination arm of BI 836845 + enzalutamide.

² Calculated based on the approximate normal distribution of the estimated log hazard ratio, i.e. assuming the log hazard ratio is normally distributed with mean log(true hazard ratio), and variance (4 / number of PFS events) (R10-4988).

³ Note that 70 events out of 80 patients can only be seen if the number of permanently censored patients is very low.

Proprietary confidential information. © 2022 Boehringer Ingelheim International GmbH or one or more of its affiliated companies. All rights reserved.

Assuming recruitment rates of 10-13 patients per month for a period of A months, the percentage of observed PFS events relative to sample size is a function of study duration T:

$$\frac{1}{2} \left[\left(1 - \frac{e^{-\lambda_1(T-A)} - e^{-\lambda_1 T}}{A\lambda_1} \right) + \left(1 - \frac{e^{-\lambda_2(T-A)} - e^{-\lambda_2 T}}{A\lambda_2} \right) \right].$$

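### For time with CTC under 5, the AUEC in SAP 7.9.3 is the wrong measure: it is in cell-days, not days, and it grows with time on treatment

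*SAP*

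**What the plan says.** The CTC item in SAP 7.9.3 names two tools: "Exploratory analyses including nonlinear function fits and AUECs will be performed". The stated purpose is a duration for each patient: "AUECs will be performed in order to quantify the time for which the cell counts remain under 5 cells per 7.5ml for each patient". The item ends with a between-arm comparison: "The measures will be compared between the treatments".

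The calculation rule appears in the cfDNA item just above, where AUEC is spelled out as area under the effect curve: "for the calculation, the linear trapezoidal method is used, as described in (3), RD_01". No other rule is given for CTC. The cfDNA AUEC is also compared between treatments, but it is planned only if feasible and has no time-below-threshold target.

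Protocol 6.2.2 sets the CTC sampling times: "Prior to study drug administration at C1D1, C2D1, C3D1, C5D1, C7D1 and every 12 weeks thereafter at C10D1, C13D1 onwards". The flow chart and Protocol 6.2.3 add a sample at EOT. EOT differs between patients, because Protocol 3.1 states: "Patients will continue treatment until disease progression, undue toxicities, or discontinuation for any other reason".

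SAP 7.9 calls the biomarker analyses purely exploratory, with no strict error control.

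**The concern.** The target is a number of days. The area under a count curve is counts multiplied by days. Two patients with the same time below 5 can have very different areas, and a patient who is never below 5 can have a smaller area than one who is below 5 for most of a year.

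The integration interval is also set by how long the patient stays on treatment. If the combination delays progression, arm A patients are sampled for longer and accumulate more area at the same CTC level. If a raw area is then read as disease burden, with lower taken as better, longer disease control counts against the arm that achieved it. What is at stake is the reading of one exploratory comparison that may inform views of CTC as an efficacy marker.

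**Working it through.** **No figure to reproduce.** The documents give no power, alpha or expected value for this comparison. The planning inputs do reproduce: ln 2 / 4.6 = 0.151 and ln 2 / 3 = 0.231 per month, as in Protocol 7.6.

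**Inputs from the documents**
- CTC samples on days 1, 29, 57, 113, 169, then every 84 days, plus EOT (Protocol 6.2.2 and flow chart).
- Planning medians (Protocol 7.6): "the estimated median PFS time in the enzalutamide arm is around 3 months", and 4.3 to 4.6 months for the combination.
- 1 month = 365.25/12 days (SAP 7), so 3 months is about 91 days and 4.6 months about 140 days.

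**Assumptions.** The documents give no on-treatment CTC levels, so every count below is assumed. PFS medians are used as a proxy for time on treatment.

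**Formula.** AUEC = sum over consecutive samples of (t[i+1] − t[i]) × (y[i] + y[i+1]) / 2. Days below 5 come from linear interpolation between the same samples.

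**Step 1: area is not duration**

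| Assumed patient | AUEC (cell-days) | Days below 5 |
|---|---|---|
| Constant 0, 140 days | 0 | 140 |
| Constant 3, 140 days | 3 × 140 = 420 | 140 |
| Constant 8, 56 days | 8 × 56 = 448 | 0 |
| 8 on day 1, 3 from day 29, EOT day 337 | 28 × 5.5 + 308 × 3 = 1078 | 11.2 + 308 = 319.2 |

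In the last row the line from 8 to 3 crosses 5 after 28 × 3/5 = 16.8 days, which leaves 11.2 days of that interval below 5.

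**Step 2: area grows with time on treatment.** At a constant count c, AUEC = c × T. With c = 3 it is 273 at 91 days and 420 at 140 days. The ratio at equal counts does not depend on c:
- 4.3/3 = 1.43
- 4.6/3 = 1.53

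For the areas to tie, arm A's counts would have to be lower by 1 − 3/4.3 = 30% to 1 − 3/4.6 = 35%.

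**Step 3: a less tidy case.** A simulation on the protocol schedule used exponential time on treatment (medians 3 and 4.6 months, capped at 22.5 months), an assumed count of 10 at baseline and EOT, and 3 in between in arm B.

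| Arm A on-treatment count | Mean AUEC, B vs A | Mean days below 5, B vs A | AUEC per day, B vs A |
|---|---|---|---|
| Equal | 561 vs 766 | 97 vs 157 | 5.15 vs 4.78 |
| 20% lower | 563 vs 659 | 98 vs 158 | 5.15 vs 4.35 |
| 40% lower | 562 vs 567 | 97 vs 162 | 5.16 vs 3.88 |

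With 40 per arm and counts 20% lower in arm A, arm A had the higher mean AUEC in 82% of simulated trials. Dividing by observed time removes the reversal. It is not neutral on its own: at equal on-treatment counts it gives 5.15 versus 4.78, because the high first and last samples weigh more in a short follow-up. Days below 5 also rise with follow-up. A common window is therefore needed in both cases.

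**Step 4: an alternative meaning of AUEC.** If the area between 5 and the curve were meant, which is not stated, it would still not be a duration. Constant 0 for 56 days gives 5 × 56 = 280, while constant 4 for 224 days gives 1 × 224 = 224.

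**The case against.** The strongest reply is that the SAP does not rely on the AUEC alone. It names nonlinear function fits first, and a fitted curve can be solved for the time it lies below 5. That stands. A reader might infer from Step 1 that the plan leaves its stated quantity unestimated, and the text does not support going that far. What remains is that the AUEC is offered for the same purpose, that the SAP does not say the fits are the source of the duration, and that the measures are compared between arms.

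A second reply is that the definition may sit elsewhere. The trapezoidal rule is written under cfDNA and points to an internal reference document that is not available here, and the copy of the SAP is incomplete. This stands as a limit: the absence of a window or normalisation is established only for the visible text. Carrying the rule over to CTC rests on AUEC being defined once, in that item.

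A third reply is that the size is illustrative. The counts are assumed, and EOT can follow toxicity or other reasons as well as progression. That also stands. The ratio at equal constant counts needs no particular CTC level, but it does need the proxy for time on treatment.

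For cfDNA only the follow-up-length problem applies, and its sampling schedule is not visible, so no specific window can be recommended for it.

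**Conclusion.** The point holds for the AUEC part of the CTC analysis. A trapezoidal area in cell-days cannot quantify time under 5, and without a common window or time normalisation it rises with time on treatment. At constant, equal counts the excess in arm A is a factor of 1.43 to 1.53, assuming that time on treatment follows the planning medians.

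A reader might go further and conclude that the better arm will look worse. The documents do not establish that. It requires a real PFS benefit, a raw AUEC and a lower-is-better reading, and the SAP fixes neither the normalisation nor the direction of benefit. The 82% figure rests on the assumed counts as well.

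Severity is low. Primary PFS is unaffected. So are the secondary CTC endpoints: reduction from 5 or more to below 5, maximum decline, and week 12 status, which has its own fixed window.

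**What to change.** In the CTC item of SAP 7.9.3:
- Replace the AUEC as the measure of time under 5 with days below 5, obtained by linear interpolation between consecutive samples or from the fitted curve. State which of the two is the main version.
- Compare arms over a common window, for example C1D1 to C3D1, which holds three scheduled samples over 56 days. State how patients who stop before the window ends are handled.
- Report days below 5 alongside each patient's sampled days. A proportion of sampled days alone is not the stated duration, and it would score an early stopper with low counts at 100%.

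If an AUEC is kept for CTC or cfDNA, divide it by the observed duration, compare arms over a common window that the biomarker's own sampling schedule supports, and state the direction of benefit.

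The cost is SAP wording and a small derivation change. CTC needs no new samples. For cfDNA the window should be chosen from its actual schedule.
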